11.8.2. Procedures for Early Withdrawal

If a subject withdraws or is removed from the study for any reason, the subject should complete an End of Study visit. Reason for withdrawal, date of the discontinuation, and date of the last dose of study drug should be recorded in the appropriate section of the eCRF. Additionally, the discontinuation visit date must be registered in IWRS. Study drug assigned to the withdrawn subject may not be assigned to another subject.

All effort should be made to have each subject complete all study visits on schedule according to the protocol. Accommodations for early or late visits in special circumstances will be considered by the Sponsor to prevent early withdrawal. Written notice (regardless of cause) is to be provided within 48 hours of the withdrawal to the Sponsor personnel or the Medical Monitor. At the time of discontinuation, every effort should be made to ensure all relevant procedures and evaluations scheduled for the final study visit are performed. Except in the case of a medical emergency, the procedures and assessments detailed in [Appendix 1](#) for Visit T3/EOS will be performed upon the discontinuation of the study.

12. ASSESSMENT OF PHARMACODYNAMICS

12.1. Pharmacodynamic Assessments

12.1.1. Sample Collection, Storage, and Shipping

Blood samples for Basic fasting lipids (LDL-C, non-HDL-C, TC, TG, and HDL-C), and Special lipids and biomarkers (apoB, hs-CRP, glucose, [REDACTED] and HbA_{1C}) will be drawn with the subject in the seated position according to the schedule of events described in [Appendix 1](#). All samples will be collected following a 10-hour fast with the exception of sample collected for the 2-hour postprandial glucose assessment as described in [Section 12.1.3](#).

Laboratory samples will be collected by appropriate clinical site personnel and then shipped according to the instructions in the laboratory manual (provided by the central laboratory). Reserve samples (serum and plasma) will be stored frozen for potential future measurement of additional BA safety and efficacy biomarkers.

12.1.2. Sample Collection, Storage, and Shipping

Blood samples for Basic fasting lipids, and Special lipids and biomarkers will be drawn with the subject in the seated position. All samples will be collected following a 10-hour fast with the exception of sample collected for the 2-hour postprandial glucose assessment as described in [Section 12.1.2](#). Laboratory samples will be collected by appropriate clinical site personnel and then shipped according to the instructions in the laboratory manual (provided by the central laboratory).

12.1.3. Two-hour Postprandial Glucose (PPG) Assessment

At Visits T1, T2, and T3 following procedures described in [Section 11.7](#); subjects will consume 1 serving of Ensure Original Vanilla breakfast drink (Abbott Laboratories: 220 calories, 32 g of total carbohydrate) at approximately 9:00 AM and site staff will record the time of the start and completion of the meal. The entire serving should be consumed within 5 minutes. A PPG blood glucose sample will be collected 2 hours ± 5 minutes after the subject begins to consume the Ensure breakfast drink and processed for plasma per the laboratory manual. The sample will be assessed by the central laboratory for glucose.

12.1.4. HOMA-IR and [REDACTED]

HOMA-IR and [REDACTED] will be calculated from fasting glucose and insulin levels determined at Visit T1 (baseline), Visit T2, and Visit T3/EOS using the following formulas described by Matthews et al.¹⁵

$$\text{HOMA-IR} = \text{fasting glucose} \times \text{fasting insulin} / 22.5$$

[REDACTED]

[figure not shown]

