6.3. Exploratory Objectives

- To assess the effect of FDC versus PBO and EZE on hemoglobin A_{1C} (HbA_{1C}), fasting glucose, [REDACTED] homeostatic model assessment of insulin sensitivity (HOMA-IR) and [REDACTED] and 2-hour postprandial glucose (PPG) in subjects with T2D treated for 12 weeks.

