17. The subject has used prohibited drugs and/or nutritional supplements within 5 weeks prior to Visit T1 (unless otherwise specified) or plans to use any of the prohibited drugs and/or nutritional supplements during the study, including but not limited to:
 - a. Statins;
 - b. Fibrates (including fenofibrate);
 - c. Niacin and derivatives;
 - d. Bile acid sequestrants;

- e. Ezetimibe (study-provided is allowed);
 - f. Apheresis;
 - g. Mipomersen or lomitapide (6 months prior to Visit S1);
 - h. Proprotein convertase subtilisin/kexin type 9 (PCSK9) inhibitors (4 months prior to Visit S1, except PCSK9 small interfering RNA (siRNA), which are prohibited if used at any time in the past);
 - i. Cholesteryl ester transfer protein (CETP) inhibitors (12 months prior to Visit S1);
 - j. Red yeast rice extract-containing products;
 - k. Omega 3 fatty acids and derivatives such as Lovaza[®] and over-the-counter (OTC) fish oil;
 - l. Systemic corticosteroids (within 5 weeks prior to Visit T1; topical and inhaled corticosteroids are allowed);
 - m. The following therapies for the treatment of T2D: rapid-acting and short-acting insulins including Lispro (HumaLog[®]), Aspart (Novalog[®]), Glulisine (Adipra[®]), Novolin R/Novolin Regular, Humulin R/Humulin Regular (except when used for basal delivery by infusion pump); injectable GLP-1 agonists such as Exenatide (Byetta, Bydureon), liraglutide (Victoza[®]), albiglutide (Tanzeum[®]) and dulaglutide (Trulicity[®]); injectable synthetic forms of amylin such as Pramlintide (Symlin); and insulin glargine/lexisenatide (Soliqua[®]) (within 3 months prior to Visit T1);
18. The subject has planned initiation of or dosing changes in the following allowed drugs before or during the study:
- a. Oral diabetes medications (within 3 months prior to Visit T1);
 - b. Intermediate-acting and long-acting insulin and insulin analogs when used for basal delivery of insulin including NPH, NovoLIN N, HumuLIN N, Glargine (Lantus), Determir (Levemir), NovoLIN 70/30, HumuLIN 70/30, NovoLog Mix 70/30 or HumuLOG Mix 70/30 (within 3 months prior to Visit T1),
 - c. Rapid-acting and short-acting insulins only when used for basal infusion pump delivery (no bolus delivery allowed) including Lispro (HumaLog[®]), Aspart (Novalog[®]), Glulisine (Adipra[®]), Novolin R/Novolin Regular, Humulin R/Humulin Regular (within 3 months prior to Visit T1),
 - d. Obesity medication (within 3 months prior to Visit T1);

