9.3.2. Allowed Medications

Use of the following medications is allowed during the study:

- oral diabetes medications if no changes in dose are made within 3 months before randomization (Visit T1/Day 1) or during the study;
- Intermediate-acting and long-acting insulin and insulin analogs when used for basal delivery of insulin including NPH, NovoLIN N, HumuLIN N, Glargine (Lantus), Determir (Levemir), NovoLIN 70/30, HumuLIN 70/30, NovoLog Mix 70/30 or HumuLOG Mix 70/30 if no changes in dose are made within 3 months prior to Visit T1;
- Rapid-acting and short-acting insulins only when used for basal infusion pump delivery (no bolus delivery allowed) including Lispro (HumaLog[®]), Aspart (Novolog[®]), Glulisine (Adipra[®]), Novolin R/Novolin Regular, Humulin R/Humulin Regular if no changes in dose are made within 3 months prior to Visit T1;
- obesity medications if no changes in dose have been made within 3 months before randomization (at Visit T1/Day 1) or during the study;
- hormone replacement therapy if no changes in dose are made within 5 weeks before randomization (at Visit T1/Day 1) or during the study;

- thyroid placement therapy if no changes in dose are made within 5 weeks before randomization (at Visit T1/Day 1) or during the study; and
- topical corticosteroids.

Short-term use of a medication for a self-limiting indication (eg, acetaminophen for a headache) may be authorized by the investigator. The maximum allowable dose of acetaminophen is 2 g/day. The investigator must make the decision to authorize use of such a medication only after consideration of the clinical situation, the potential for masking symptoms of a more significant underlying event, and whether use of the medication will compromise the outcome or validity of the study.

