### **5.4 Exploratory Analyses**

For exploratory endpoints (change and percent change from baseline to Week 12 in HbA1C, fasting glucose,

HOMA-IR index, and 2-hour PPG), the data will be analyzed in the similar fashion as for the primary endpoints. For fasting plasma glucose,

HbA1C, 2-hour PPG and the baseline is the predose Day 1/Week 0 (Visit T1) value. If no value is available at Visit T1, then the last value prior to first dose of IMP will be used as baseline.

Sensitivity analyses will be used to examine if the potential data issues previously identified at 3 sites in Study (Sites ) impact the

Confidential

Page 20 of 38

Version 1.3, July 23, 2019 Statistical Analysis Plan

efficacy results of this study. The sensitivity analysis will repeat selected key analyses including all FAS subjects, as listed below:

- 1. Patient Disposition
- 2. Demographic and Baseline Characteristics Full Analysis Set
- 3. Summary Statistical Analysis of Percent Change from Baseline in Primary Efficacy Endpoints at Week 12 Full Analysis Set
- 4. Summary Statistical Analysis of Percent Change from Baseline in Secondary Efficacy Endpoints at Week 12 Full Analysis Set
- 5. Statistical Analysis of Median Percent Change from Baseline in hs-CRP and TG at Week 12 via Non-parametric Approach (Observed Data) Full Analysis Set
- 6. Statistical Analysis of Percent Change from Baseline in HbA1C Full Analysis Set
- 7. Statistical Analysis of Percent Change from Baseline in Fasting Glucose Full Analysis Set

8.			
9.			

Additional exploratory and sensitivity analyses may be performed as needed.

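### HOMA-IR is built from measured fasting insulin, yet stable insulin users are enrolled and SAP 5.4 shows no restriction to subjects in whom the index measures insulin resistance.

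*Protocol*

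**What the plan says.** - **Index.** Protocol 12.1.4: HOMA-IR "will be calculated from fasting glucose and insulin levels determined at Visit T1 (baseline), Visit T2, and Visit T3/EOS", as the product of the two divided by 22.5. No exception for insulin-treated subjects is visible.
- **Who is enrolled.** Protocol 9.3.2 allows "Intermediate-acting and long-acting insulin and insulin analogs when used for basal delivery of insulin". The same item includes premixed products: "NovoLIN 70/30, HumuLIN 70/30, NovoLog Mix 70/30 or HumuLOG Mix 70/30 if no changes in dose are made within 3 months" before T1. It also allows "Rapid-acting and short-acting insulins only when used for basal infusion pump delivery (no bolus delivery allowed"), under the same 3-month condition.
- **Dose stability.** Exclusion 18 in Protocol 8.2 removes a subject if "The subject has planned initiation of or dosing changes in the following allowed drugs before or during the study", and it names these insulins. Inclusion 3 in Protocol 8.1 requires stable diabetes medication for at least 3 months.
- **Fasting draw.** Protocol 8.3 permits concomitant medication before the sample. Protocol 11.7 and 13.6.1 describe a water-only fast and do not mention insulin. No visible text sets an interval since the last insulin dose or addresses a running pump.
- **Analysis.** SAP 5.4: "HOMA-IR index, and 2-hour PPG), the data will be analyzed in the similar fashion as for the primary endpoints". Under SAP 5.3 and 5.3.1 that means ANCOVA on treatment and baseline value in the Efficacy Analysis Set (EAS), which is the FAS without three sites. Insulin use is not among the six subgroup variables in SAP 5.2.5, and SAP 4.3 states no stratification by it.
- **Objective.** The protocol synopsis names HOMA-IR as the measure of insulin resistance. Protocol 6.3 and SAP 3.1 use the same index but word it as insulin sensitivity.

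**The concern.** The product of fasting glucose and fasting insulin reads as resistance only when the insulin in the sample is the subject's own response to the glucose. In a subject on basal, premixed or pump insulin there are two possibilities, and the visible text does not say which applies because it does not describe the insulin assay. If the assay detects injected insulin, the index includes the dose and the time since it was given. If it does not, the index reflects own secretion suppressed by injected insulin, which is not comparable with the value in a non-user.

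Following the plan as written therefore pools two different quantities under one insulin-resistance objective. Percent changes in users are diluted, and unplanned dose changes or variation in time since dosing add noise unrelated to the study drug. A null or small HOMA-IR result could not be read as showing no effect on resistance.

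**Working it through.** The documents state no effect size, SD or power for HOMA-IR, so there is no planned figure to reproduce. The check is the text set out above plus algebra on the formula in 12.1.4. The injected share of assayed insulin, the share of insulin users and all SDs below are assumptions.

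**Step 1: one subject, percent change.** Let G be glucose, E own insulin, X detected injected insulin, and f = X/(E+X) at baseline. HOMA-IR = G(E+X)/22.5.

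- Own insulin falls by r, with G and X constant: percent change = −r(1−f). For r = 20%: −20% at f = 0, −15% at f = 0.25, −10% at f = 0.50, −5% at f = 0.75.
- Injected insulin shifts by e, with G and E constant: percent change = f·e. For e = 30%: 7.5%, 15% and 22.5% at f = 0.25, 0.50 and 0.75.
- A change in glucose alone passes through in full at any f.

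**Step 2: one subject, absolute change.** The SAP analyses change as well as percent change. Take G = 9 mmol/L and E = 12 µU/mL, with X = 0 or 20.

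- Baseline: 9×12/22.5 = 4.8 and 9×32/22.5 = 12.8.
- E falls 20% to 9.6: 9×9.6/22.5 = 3.84 and 9×29.6/22.5 = 11.84. Both fall by 0.96, which is −20% without and −7.5% with injected insulin.
- Glucose falls to 8 instead: 8×12/22.5 = 4.27 (−0.53) and 8×32/22.5 = 11.38 (−1.42). The same glucose change counts 32/12 = 2.67 times as much in the user.

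Stable injected insulin therefore dilutes the insulin component of percent change. In absolute change it leaves that component alone but inflates the glucose component.

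**Step 3: whole trial.** With user share q, the same r in users and non-users, and constant G and X, the mean percent change is −r(1 − q·f). The relative dilution is q·f: 0.10×0.25 = 2.5% at the low end, 0.20×0.50 = 10% in the middle, and 0.40×0.75 = 30% at the high end.

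**Step 4: does restriction help precision?** Take 78 per arm (SAP 4.4; Protocol 14.2 has 56) and equal mean change in users and non-users. SE ratio, restricted over all = sqrt{(s₀²/n_nonusers) / ([(1−q)s₀² + q·s₁²]/78)}, where s₀ and s₁ are the SDs of non-users and users.

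- s₀ = 0.35, s₁ = 0.80: 0.885 (q = 10%, n = 70), 0.826 (20%, n = 62), 0.791 (30%, n = 55).
- s₀ = 0.35, s₁ = 0.50, q = 20%: pooled variance 0.148, ratio 1.02, so the SE is about 2% larger.
- Break-even: s₁/s₀ = sqrt[(2−q)/(1−q)] = 1.45, 1.50 and 1.56 at q = 10%, 20% and 30%.

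The direction depends on SDs that the documents do not give. These values are also on a log-change scale, which the SAP does not specify for HOMA-IR.

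**Step 5: subjects lost by restricting.** At q = 10%, 20%, 30% and 40%, 78 per arm leaves 70, 62, 55 and 47, and 56 per arm leaves 50, 45, 39 and 34. An effect with 80% power at 78 per arm (two-sided 0.05) would have 75.6%, 70.5%, 65.3% and 58.5% in non-users alone. This counts only the smaller n and ignores the dilution that restriction removes.

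**The case against.** Several points limit the concern, and most of them stand.

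- **Titration.** A reader of 9.3.2 alone might infer that insulin doses may change freely after T1, because the oral-drug item extends stability through the study and the insulin items stop at T1. Exclusion 18 bars planned insulin changes during the study too. Only unplanned changes remain open.
- **Levels versus change.** A jump from 4.8 to 12.8 looks dramatic, but it compares two levels. The endpoint is change from baseline, and stable injected insulin sits in both values. It mainly dilutes percent change and does not create a spurious rise.
- **Precision.** A reader might infer that excluding users narrows the interval. Step 4 shows that this holds only if the users' SD is about 1.5 times the non-users' SD or more, which cannot be checked.
- **Bias between arms.** Allocation is randomized and double-blind. Chance imbalance in insulin use is ordinary sampling variation that the interval covers, not systematic bias.
- **No signal in users.** This goes too far. Glucose still moves the index in full, and the insulin component is attenuated rather than abolished.
- **Existing reporting.** SAP 5.2.8 summarizes concomitant medication by arm and ATC class, SAP 5.2.4 summarizes prior diabetes therapies by type, and SAP 5.4 permits additional analyses.
- **Redaction.** Text beside HOMA-IR is blacked out or missing in Protocol 12.1.4 and 14.7 and in SAP 5.4. A restriction or companion marker could be there.

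None of this restores the meaning of the index in insulin users. Randomization makes the arms comparable on average but does not turn injected insulin into a measure of resistance, and adjusting for a baseline with the same defect does not either.

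**Conclusion.** The point holds as one of validity. On the visible text, stable insulin users enter the HOMA-IR analysis with nothing to separate them, and in them the index does not measure what the objective names.

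Its size is uncertain. Over assumed ranges of 10% to 40% users and 25% to 75% injected share, the mean percent change driven by own insulin is diluted by 2.5% to 30% in relative terms. That rests on constant glucose and injected insulin, the same true change in users and non-users, and an assay that detects the injected insulin. If the assay does not detect it, this calculation does not apply, but the values remain non-comparable with those of non-users.

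The documents do not support claims of systematic bias between arms, unrestricted titration or a sure gain in precision. HOMA-IR is exploratory and outside the co-primary success rule, so the LDL-C conclusions are unaffected. The change is worth making because it is cheap and determines whether the HOMA-IR result can be interpreted.

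**What to change.** In SAP 5.4:

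1. Define the main analysis of HOMA-IR, and of any other index built on fasting insulin, in EAS subjects not using exogenous insulin at baseline.
2. Take the flag from medication ongoing at the first dose of double-blind study drug. Protocol 9.3 already collects concomitant medication with daily dose and start and stop dates.
3. Report the number of baseline insulin users by arm.
4. Keep the all-subject EAS result as supportive.
5. Handle insulin started after T1 in a sensitivity analysis, not by exclusion. Starting insulin is a post-randomization event that treatment could affect, so excluding on it would break the randomized comparison. A baseline flag avoids this.

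The cost is a few sentences in the SAP, one derived flag and fewer subjects for an exploratory endpoint, for example 62 instead of 78 per arm if 20% use insulin (assumed). No new data and no change to treatment rules are needed. If the redacted text already contains such a restriction, check only that it rests on baseline use.

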12.1.5. Exploratory Biomarker Measurement

Additional exploratory safety, efficacy, or potential biomarkers may be assayed from serum and plasma blood samples collected at Visits T1 and T3 and stored frozen, reserved for potential future measurement of potential biomarkers.

12.1.6. Clinical Laboratory Parameters (Basic Fasting Lipids, Special Lipids and Other Biomarkers)

Blood specimens for basic fasting lipids, special lipids, and other biomarker laboratory assessments will be collected as shown in Table 2.

Table 2: Clinical Laboratory Parameters (Basic Fasting Lipids, Special Lipids and Other Biomarkers)

Clinical Laboratory Test	Clinical Laboratory Test

Basic Fasting Lipid Parameters
 
 • Calculated low-density lipoprotein cholesterol (LDL-C) • Non-high-density lipoprotein cholesterol (non-HDL-C) • Total cholesterol (TC) • Triglycerides (TG) • High-density lipoprotein cholesterol (HDL-C) 
Additional Samples
 
 • Reserve blood samples for potential future measurement of biomarkers 	
Special Lipids and Other Biomarkers
 
 • High-sensitivity C-reactive protein (hs-CRP) • Apolipoprotein B (apoB) • Glucose •  • Hemoglobin A_{1C} (HbA_{1C})

13. ASSESSMENT OF SAFETY

13.1. Demographics and Medical History

Demographic data and a medical history will be obtained from the subject at Visit S1/Day -42. Conditions that are relevant and/or clinically significant should be captured with at least a start date and an indication of whether the condition is ongoing or resolved. All surgeries, regardless of date, should be reported.

13.2. Vital Signs

Systolic blood pressure, diastolic blood pressure, and pulse rate will be recorded according to the schedule of events ([Appendix 1](#)). Measurements should be taken after subject has been seated quietly for at least 5 minutes in a chair with the back supported, the feet flat on the ground, and the arms bared and supported at heart level.

Blood pressure will be obtained using a calibrated, fully automated machine with a cuff that is appropriate to the size of the upper right arm. If a fully automated machine is not available, blood pressure may be measured manually. The same method (either automated or manual) and the same arm (right or left) must be used throughout the study.

13.3. Weight, Height, and Body Mass Index

Height will be measured in centimeters (cm) at Visit S1 only. Weight will be measured in kilograms (kg) on a calibrated scale in the morning while fasting, in street clothing, and after voiding at Visit S1, T1, and T3/EOS.

Body mass index will be calculated as the weight in kilograms divided by the height in square meters (kg/m^2).

13.4. Physical Examination

A complete PE will be performed according to the schedule of events ([Appendix 1](#)) or at early termination from the study. A complete PE includes an assessment of the following:

- general appearance;
- skin;
- eyes, ears, nose, and throat (EENT);
- head/neck;
- extremities;
- musculoskeletal examination;
- respiratory examination;
- cardiovascular assessment, including rhythm and presence of cardiac abnormalities;

- abdominal examination;
- neurologic examination to record the presence of abnormalities in mental status, motor, and sensory function; and
- any additional assessments necessary to establish baseline status or evaluate symptoms or adverse experiences.

Documentation of the PE will be included in the source documentation at the study site. Changes from baseline (Visit T1/Day 1) in PE findings that meet the definition of an AE will be recorded on the appropriate eCRF.

13.5. 12-Lead Electrocardiograms

A single 12-lead ECG will be obtained during screening at Visit S2. Additional 12-lead ECGs may be obtained at other times if clinically indicated. The ECG should be obtained after the subject has rested quietly in the supine position for at least 10 minutes.

13.6. Clinical Laboratory Tests

13.6.1. Clinical Safety Laboratory Parameters

Blood and urine specimens for safety laboratory assessments will be collected as shown in [Table 3](#).

Table 3: Clinical Safety Laboratory Evaluations

Clinical Laboratory Test	Clinical Laboratory Test
Hematology 
 • Hematocrit (Hct) • Hemoglobin (Hgb) • Mean corpuscular hemoglobin (MCH) • Mean corpuscular hemoglobin concentration (MCHC) • Mean corpuscular volume (MCV) • Platelet count • Red blood (RBC) cell count • White blood (WBC) cell count with differential (absolute and %) 	Blood Chemistry (serum, fasting) 
 • Albumin (Alb) • Alkaline phosphatase (ALK-P) • Alanine aminotransferase (ALT; serum glutamic pyruvic transaminase [SGPT]) • Aspartate aminotransferase (AST; serum glutamic oxaloacetic transaminase [SGOT]) • Blood urea nitrogen (BUN) • Calcium (Ca) • Carbon dioxide (CO₂) • Chloride (Cl) • Creatinine • Creatine kinase (CK) • Glucose • Lactate dehydrogenase (LDH) • Phosphorus • Potassium (K) • Sodium (Na) • Total bilirubin (TB)^a • Total protein • Uric acid
Urinalysis (Dipstick) 
 • Clarity • Bilirubin • Color • Glucose • Ketones • Leukocyte esterase • Nitrite • Occult blood • pH • Protein • Specific gravity • Urobilinogen 	Coagulation (Visit S1 for all subjects, Visit T1 and 3-7 days after Visit T1 in subjects receiving anticoagulation therapy only) 
 • Prothrombin time (PT) • International normalized ratio (INR)
Urinalysis (Microscopic)-only if urine dipstick abnormal 
 • Bacteria • Casts • Crystals • Epithelial cells • RBC • WBC 	

Table 3: Clinical Safety Laboratory Evaluations

Clinical Laboratory Test	Clinical Laboratory Test
Other Screening Labs	Additional samples

 • Hepatitis B surface antigen (HBsAg) • Hepatitis C virus (HCV)^b • Serum pregnancy test (only for females of childbearing potential) • Follicle-stimulating hormone (FSH; Females <55 years and ≥1 year without menses) • Urine pregnancy test prior to randomization (for female of child bearing potential) • Thyroid-stimulating hormone (TSH) 	
 • Hemoglobin A_{1C} (HbA_{1C})

^a If TB ≥1.2 × ULN, a reflex indirect (unconjugated) bilirubin will be obtained.

^b If hepatitis C antibody (HCV-AB) is positive, a reflex HCV RNA will be performed to rule out active disease.

Subjects will be instructed to fast for a minimum of 10 hours before each blood draw; only water will be permitted during the fasting period. If the subject has not fasted for a minimum of 10 hours before the study visit, the blood sample will not be drawn at that visit. The reason for any missing blood samples will be documented.

When vital signs and blood samples for safety laboratories are to be collected at the same time, measurement of vital signs should precede collection of blood samples.

